### 3.4 Safety Review Committee

A SRC oversees the safety of all phases of the study. During the phase 1b dose optimization (Part 4) of the study, the SRC convenes at appropriate intervals (when all 3 or 6 subjects in a given cohort are evaluable for DLT determination) to review all available safety data in a cohort, cumulative information from all dosed subjects, and any new preclinical information, as in phase 1a. The SRC renders decisions on dose escalation and other safety aspects of the study. All actions of the SRC are documented in written minutes.

During phase 1b dose optimization (Part 2 and Part 3), any significant safety and tolerability issues observed based on medical monitoring and pharmacovigilance signal detection can be discussed at SRC for recommendation on any actions taken. The SRC can also convene to discuss any individual patient cases brought forth for advice by the treating investigators or the sponsor. The SRC will extend its responsibility under Amendment 9 to review both safety and efficacy data to recommend a decision as to whether or when to proceed with the Part 3 CTCL and PTCL cohorts to next stage per the Simon's 2-stage design in parallel to the Part 4 dose optimization phase of the study. The membership of the SRC may vary between different phases of the study and will be documented in the SRC Safety Committee Charter.

During phase 1a, the SRC consisted of the Chief Medical Officer/Medical Monitor, Head of Clinical Operations, all enrolling Investigators, and other Sponsor personnel as appropriate. Under Amendment 9, the SRC will involve all enrolling investigators in the data review and discussion but due to the size of the participating sites, only selected 3-5 investigators will function as the official members of the SRC and will therefore have the voting right. All discussions and decisions of the SRC will be documented in writing.

### **3.5 Number of Subjects**

The dose escalation portion of the study is estimated to enroll up to 36 subjects with an advanced lymphoma. The dose expansion phase 1b (Part 2) will enroll 12–15 subjects per cohort type. If preliminary evidence of clinical benefit is observed in association with acceptable tolerability, one or more hematologic disease-specific cohorts may be expanded up to a maximum of 40 subjects. For the dose expansion phase 1b (Part 3), the number of subjects in the CTCL and PTCL cohorts will be enrolled based upon a Simon optimal 2-stage design with a maximum of 35 subjects in each cohort.

In addition, approximately 25 subjects will be enrolled for the phase 1b dose optimization (Part 4). The total number of subjects enrolled in the study is approximately 285 subjects (see [Section 8.3](#) for details).

### **3.6 Investigational Sites**

Approximately 20 institutions will enroll subjects into this study.

### **3.7 Study Duration**

The dose-escalation phase of the study is expected to run for approximately 18 months and the expansion phase of the study for approximately 5 years.

## 4 SELECTION OF STUDY POPULATION

Potential subjects must sign an informed consent form before any study-specific screening tests may be conducted. Screening tests are described in [Section 7.1](#).

### 4.1 Inclusion Criteria

#### *Phase 1a Escalation (Completed and now Closed)*

1. Histologically documented, advanced lymphoma after the failure of at least 2 prior therapies with at least one site of measurable disease ( $\geq 1.5$  cm in the long axis or  $\geq 1.0$  cm in both the long and short axis). Additionally, subjects with NHL (indolent and aggressive B-cell lymphomas) should have failed CD20-targeted therapy.
2. Adequate hematologic status (in the absence of transfusion and growth factor support for at least 28 days), defined as:
  - absolute neutrophil count (ANC)  $\geq 1.5 \times 10^9/L$
  - platelets  $\geq 75 \times 10^9/L$
  - hemoglobin  $\geq 10 \text{ g/dL}$

#### *Phase 1b Expansion (Selected Cohorts Currently Open for Parts 2 and 3)*

1. Advanced measurable malignancy documented by histology, cytology, flow cytometry, fluorescent in situ hybridization (FISH) or polymerase chain reaction (PCR) methodology in one of the following categories:
  - (closed) Small cell lung cancer (SCLC) (measurable disease by the Response Evaluation Criteria in Solid Tumors [RECIST], Version 1.1)
  - Histologically documented, advanced lymphoma after the failure of at least 2 prior systemic therapies with at least one site of measurable disease ( $\geq 1.5$  cm in the long axis or  $\geq 1.0$  cm in both the long and short axis). Additionally, subjects with CD20-positive NHL (indolent and aggressive B-cell lymphomas) should have failed CD20-targeted therapy
    - Indolent B-cell lymphoma (see [Appendix A](#))
    - Aggressive B-cell lymphoma (see [Appendix A](#))
    - Classic Hodgkin lymphoma
      - Patients with cHL should have failed at least one checkpoint inhibitor therapy before enrolling to the nivolumab combination cohort
  - Peripheral T-cell lymphoma ([PTCL] as defined by mature T- and NK-cell neoplasms per WHO and CTCL, see [Appendix A](#)), having failed at least 1 prior systemic therapy. Subjects with PTCL must have at least

1 site of measurable disease ( $\geq 1.5$  cm in the long axis or  $\geq 1.0$  cm in both the long and short axis)

- CTCL (both MF and SS):
  - Failed at least 2 prior systemic therapies for CTCL. Systemic therapy does not include local radiation therapy or topical agents
  - Malignancy is measurable per global CTCL criteria (Olsen, 2011)
  - History of histologically-documented diagnosis of CTCL stage IIB to IVB (Olsen, 2011)
- (closed) B-cell or T-cell acute lymphoblastic leukemia (ALL):
  - First or greater bone marrow relapse from complete remission, or
  - Any bone marrow relapse after allogeneic transplant, or
  - Absence of complete remission after 2 induction attempts employing standard regimens, or
  - Ph+ B-ALL if subjects are intolerant to or ineligible to receive tyrosine kinase inhibitor therapy or have progressed after at least one line of this therapy
- (closed) CLL: subjects should have failed at least 2 prior therapies, including CD20-targeted therapy
- (closed) Multiple myeloma (MM): subjects should have failed at least 3 prior therapies, including an immunomodulatory drug (IMID) and proteasome inhibitor-based therapy and have measurable disease as defined as 1 or more of the following:
  - serum M-protein  $> 0.5$  g/dl and/or
  - urine M-protein  $> 200$  mg/24 hours and/or
  - in subjects who do not meet these criteria, serum free light chains (FLC)  $> 100$  mg/L (involved light chain) and abnormal ratio (FLC kappa/FLC lambda)
  - biopsy-proven plasmacytoma
- (closed) AML, with the exception of AML M3 using the French American British (FAB) classification (i.e., acute promyelocytic leukemia [APL]):
- (closed) MDS of WHO classifications RAEB-1 (refractory anemia with excess blasts) and RAEB-2
- (closed) BCR/ABL1-negative myeloproliferative neoplasm (MPN) or myeloproliferative/myelodysplastic overlap neoplasm (MPN/MDS) per the revised 2016 WHO criteria, including:
  - chronic phase (CP) (defined as peripheral blood and bone marrow  $< 10\%$  blasts) primary myelofibrosis or post-essential

thrombocythemia (post-ET) or post-polycythemia vera (post-PV) myelofibrosis

- if the diagnosis is Myelofibrosis-CP, must have Dynamic International Prognostic Scoring System (DIPSS) intermediate-2/high risk disease (Passamonti et al., 2010) and either be: 1) intolerant/resistant to ruxolitinib or 2) ineligible for ruxolitinib therapy, as determined by the treating Investigator
- accelerated phase/blast phase MPN (MPN-AP/BP) (defined as either a peripheral blood or bone marrow with  $\geq 10\%$  blasts)
  - if the diagnosis is MPN-AP/BP, must have progressive/resistant disease after treatment with a DNA methyl transferase 1 (DNMT1) inhibitor therapy (e.g. azacitidine or decitabine), as determined by the treating Investigator
- chronic myelomonocytic leukemia (CMML) -1 or 2 characterized by
  - $>1 \times 10^9/L$  monocytes and 2-19% blasts in peripheral blood or Auer rods and
  - dysplasia in  $\geq 1$  hematopoietic line and 5-19% marrow blasts or Auer rods
- (closed) Subjects with MPN or MPN/MDS must not be eligible to proceed with hematopoietic stem cell transplantation (HSCT) and must have:
  - for MPN, an indication to treat with cytoreductive drugs (e.g. hydroxyurea, anagrelide, interferon, ruxolitinib, etc.), according to the judgment of the treating physician
  - for MPN, documentation of inadequate response or intolerance to first line therapy, which includes at least one cytoreductive drug (e.g. hydroxyurea, anagrelide, interferon, ruxolitinib, etc.)
  - for CMML, documentation of inadequate response or intolerance to first line therapy, which includes at least one hypomethylating agent

2. Hematologic status as follows (transfusions not permissible to achieve these levels within 14 days prior to the first dosing of study drug):

- ANC  $\geq 1 \times 10^9/L$  (not applicable to subjects with AML, ALL, MDS, or MPN/MDS)
- platelets  $\geq 75 \times 10^9/L$  ( $\geq 50 \times 10^9/L$  if the patient has bone marrow involvement)
- hemoglobin  $\geq 9 \text{ g/dL}$

*Phase 1b Expansion (Dose Optimization Part 4)*

1. Histologically confirmed diagnosis of CTCL (both Mycosis Fungoides and Sezary Syndrome):
  - Failed at least 2 prior systemic therapies for CTCL (systemic therapy does not include local radiation therapy or topical agents)
  - Malignancy is measurable per global CTCL criteria (Olsen, 2011)
  - History of histologically-documented diagnosis of CTCL stage IB to IVB (Olsen, 2011)
3. Hematologic status as follows (transfusions not permissible to achieve these levels within 14 days prior to the first dosing of study drug):
  - ANC  $\geq 1 \times 10^9/L$
  - platelets  $\geq 75 \times 10^9/L$
  - hemoglobin  $\geq 9 \text{ g/dL}$

*Both Phases*

1. Male or female 18 years of age or older
2. Availability of fresh or archived tumor tissue for immunohistochemical studies. Archival tissue may be used provided it was obtained subsequent to the last prior anti-cancer therapy. For subjects with SS, peripheral blood is acceptable.
3. Relapsed or refractory disease that has previously progressed on, or is currently progressing on standard anticancer therapy or for whom no other approved conventional therapy exists
4. Eastern Cooperative Oncology Group (ECOG) performance status of 0, 1, or 2 (see [Appendix B](#))
5. Adequate coagulation function, defined as:
  - International Normalized Ratio (INR)  $< 1.5 \times$  the upper limit of normal (ULN) for that laboratory
  - partial thromboplastin time  $< 1.5 \times$  ULN
  - subjects receiving anticoagulation therapy must be on a stable dose with monitoring studies within therapeutic range per local institutional standards
6. Adequate hepatic function, defined as:

- total bilirubin < 1.5 x ULN unless considered due to Gilbert's disease
- alanine aminotransferase (ALT) and aspartate aminotransferase (AST) < 1.5 x ULN or < 3 x ULN with documented liver metastases

7. Adequate renal function, defined as estimated serum creatinine clearance > 30 mL/minute calculated using the Cockcroft-Gault equation (see [Appendix E](#)).
8. Recovery from the toxicities of previous anticancer drugs or radiotherapy to Grade 0 or 1 (or to baseline grade if condition was pre-existing)
9. Commitment from male and female subjects of reproductive potential to use, from the time of screening through 60 days after the last dose of TTI-621, either:
  - one highly effective method of contraception, including hormonal contraceptives (e.g., combined oral contraceptives, patch, vaginal ring, injectables, and implants), intrauterine device (IUD) or intrauterine system (IUS), vasectomy, or tubal ligation

OR

- at least 2 effective methods of contraception, including male condom, female condom, cervical cap, diaphragm, or contraceptive sponge

OR

- abstain from sex during study participation and for 60 days after the last dose of TTI-621

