### *Peripheral T-cell lymphoma*

- Adult T-cell leukemia/lymphoma
- Extranodal NK-/T-cell lymphoma, nasal type
- Enteropathy-associated T-cell lymphoma
- Monomorphic epitheliotropic intestinal T-cell lymphoma
- Hepatosplenic T-cell lymphoma

- Subcutaneous panniculitis-like T-cell lymphoma
- Primary cutaneous anaplastic large cell lymphoma
- Primary cutaneous gamma delta+ T-cell lymphoma
- Primary cutaneous CD8+ aggressive epidermotropic cytotoxic T-cell lymphoma
- Primary cutaneous acral CD8+ T-cell lymphoma
- Peripheral T-cell lymphoma, NOS
- Angioimmunoblastic T-cell lymphoma
- Follicular T-cell lymphoma
- Nodal peripheral T-cell lymphoma with TFH phenotype
- Anaplastic large-cell lymphoma, ALK+
- Anaplastic large-cell lymphoma, ALK-
- Breast implant-associated anaplastic large-cell lymphoma

\* This list is representative and is not intended to be exhaustive/include all types of indolent or aggressive B-cell or T-cell lymphomas that may be enrolled on study

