### Appendix D. Table 3. Response Assessments by Malignancy Type

Radiographic disease assessments for CTCL and PTCL will be submitted for central review for those subjects enrolled to phase 1b Part 3. The subjects enrolled to phase 1b Part 4 cohorts will not require submission of scans for central review in real time but retrospective submissions might be requested by sponsor.

Central photography will be utilized for CTCL patients for both phase 1b Part 3 and Part 4.

Disease and Assessments	Screening	Wk 8 	Wk 12 	Wk 16 1+	EOT
Lymphoma (including PTCL)					
PET/CT scan (PTCL: local and central review for phase 1b Part 3 only)	X	X		Weeks 16, 24, and every 12 weeks thereafter	X
Spleen assessment	X	X		Weeks 16, 24, and every 12 weeks thereafter	X
Bone marrow biopsy a	X	X		Weeks 16, 24, and every 12 weeks thereafter	X
Cutaneous T-Cell Lymphoma					
Skin assessment (mSWAT and CAILS)	X	X		Weeks 16, 24, and every 12 weeks thereafter	X
Radiographic imaging (central for CTCL for phase 1b Part 3 only) b	X	X		Weeks 16, 24, and every 12 weeks thereafter	X
Photography of disease (central for CTCL for phase 1b Part 3 and Part 4) k	X	X		Weeks 16, 24, and every 12 weeks thereafter	X
Blood assessment (pathology and flow cytometry): local and central (CTCL) for phase 1b Part 3 only c	X	X		Weeks 16, 24, and every 12 weeks thereafter	X
Spleen and liver assessment	X	X		Weeks 16, 24, and every 12 weeks thereafter	X
Acute Leukemia (AML and ALL)					
Bone marrow aspirate or biopsy d	X	X		Weeks 16, 24, and every 12 weeks thereafter	X
Cytogenetic evaluation e	X	X		Weeks 16, 24, and every 12 weeks thereafter	X
Molecular and/or flow cytometric evaluation f	X	X		Weeks 16, 24, and every 12 weeks thereafter	X
Myelodysplastic Syndrome g					
Bone marrow biopsy	X	X		Week 16, 24, and every 12 weeks thereafter	X
Peripheral blood (including blasts)	X	X		Week 16, 24, and every 12 weeks thereafter	X
Cytogenetic evaluation h	X	X		Week 16, 24, and every 12 weeks thereafter	X
MDS/MPN Overlap (including CMML)					

Disease and Assessments	Screening	Wk 8 	Wk 12 	Wk 16  +	EOT
Bone marrow biopsy	X	X		Week 16, 24, and every 12 weeks thereafter	X
Peripheral blood (including blasts and neutrophil precursors)	X	X		Week 16, 24, and every 12 weeks thereafter	X

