### **3.7.3 Organ system-specific overall response rate**

In subjects with CTCL and PTCL (in Parts 3 and 4), the organ system-specific response rates will be presented by: in skin, lymph nodes, blood, and visceral organs. (Olsen, 2011)

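### The PTCL entry criterion names CTCL, so MF/SS subjects could be counted in the PTCL Simon decision; SAP 3.7.3 also promises PTCL skin and blood rates that the schedule does not support

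*Protocol*

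**What the plan says.** **Eligibility.** In Protocol 4.1, under Phase 1b Expansion (Parts 2 and 3), the PTCL bullet reads "as defined by mature T- and NK-cell neoplasms per WHO and CTCL", "having failed at least 1 prior systemic therapy", and requires one measurable site (at least 1.5 cm in the long axis, or at least 1.0 cm in both axes). The adjacent bullet covers CTCL, both MF and SS, and requires "Failed at least 2 prior systemic therapies for CTCL" and "History of histologically-documented diagnosis of CTCL stage IIB to IVB".

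**Use of the cohorts.** Protocol 8.3 and 8.4.7 and SAP 1.2.4 give each cohort its own Simon two-stage test: stop at 2 or fewer responders of 18, and reject the drug for that indication at 6 or fewer of 35. Under Protocol 7.14.1, PTCL is assessed by Lugano, while a CTCL response is a partial or complete response in any one organ system.

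**Organ-system response.** SAP 3.7.3 states: "In subjects with CTCL and PTCL (in Parts 3 and 4), the organ system-specific response rates will be presented by: in skin", and goes on to lymph nodes, blood and visceral organs. In Appendix D Table 3, the block that includes PTCL lists "PET/CT scan (PTCL: local and central review for phase 1b Part 3 only"), spleen assessment and bone marrow biopsy. Skin scoring (mSWAT and CAILS) and the blood assessment are listed only in the CTCL block. Footnote d to Appendix D Table 1 also restricts mSWAT, CAILS and photographs to CTCL subjects.

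**The concern.** Two adjacent bullets set different entry conditions for the same disease. A subject with MF or SS who misses the CTCL bar on prior therapy or stage can satisfy the PTCL bullet, provided there is a measurable site. A subject who meets the CTCL bar and has such a site satisfies both. No rule then says where that subject is counted.

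The PTCL Simon test is meant to say whether the drug merits further testing in PTCL. If its 18 or 35 subjects include MF/SS, the stated error rates no longer refer to PTCL alone, and the boundaries leave little room for a misplaced subject.

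Separately, a planned secondary display (skin and blood response rates in PTCL) has no scheduled input.

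**Working it through.** **1. The plan's own design.** Inputs from Protocol 8.3: p0 = 10%, p1 = 30%, n1 = 18, r1 = 2, N = 35, r = 6.

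- Probability of early termination at 10%: sum over x = 0, 1, 2 of C(18,x) × 0.1^x × 0.9^(18−x) = 0.734.
- Expected N at 10%: 18 + (1 − 0.7338) × 17 = 22.53.
- Probability of passing: sum over x1 ≥ 3 of P(X1 = x1) × P(X2 ≥ 7 − x1), with X2 from 17 subjects. This is 0.047 at 10%, and 0.902 at 30% (beta 0.098).

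All four printed figures reproduce (0.734, 22.53, 0.047, 0.098). The design arithmetic is sound. The question is who is counted.

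**2. The criteria applied literally.**

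| Subject, with a site of at least 1.5 cm | CTCL bullet | PTCL bullet |
|---|---|---|
| MF/SS, stage IIB–IVB, 1 prior therapy | fails | passes |
| MF/SS, below stage IIB, 1 or more prior therapies | fails | passes |
| MF/SS, stage IIB–IVB, 2 or more prior therapies | passes if also measurable by the CTCL criteria | passes |

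**3. Does anything else close the overlap?**

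- The single-cohort rule in Protocol 3.3.1 applies only to a subject with more than one malignancy.
- Central tissue review in Part 3 (Protocol 7.1) confirms the diagnosis but is not needed before enrollment. Confirming MF would not by itself make the subject ineligible, because the PTCL bullet names CTCL.
- The other descriptions conflict with the bullet. The Synopsis (Part 3) and section 3.3.1 define PTCL by the WHO categories without adding CTCL. The Synopsis eligibility text gives the one-therapy allowance to PTCL alone. Appendix A lists MF and SS only under CTCL.

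**4. Size.** One subject is 1/18 = 5.6 percentage points at Stage 1 and 1/35 = 2.9 at the end.

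To show what a mixed cohort could do, let k of the 35 be MF/SS, split equally between stages, with response rate q, and let true PTCL response be 10%. Then X1 = Bin(18 − k/2, 0.10) + Bin(k/2, q) and X2 = Bin(17 − k/2, 0.10) + Bin(k/2, q). The chance of passing is P(X1 ≥ 3 and X1 + X2 ≥ 7). Both k and q are assumptions; the documents give neither.

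| MF/SS among 35 | q = 20% | q = 30% | q = 40% |
|---|---|---|---|
| 0 | 0.047 | 0.047 | 0.047 |
| 4 | 0.075 | 0.110 | 0.152 |
| 8 | 0.112 | 0.208 | 0.334 |
| 12 | 0.157 | 0.334 | 0.544 |

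The error can also run the other way. If true PTCL response is 30% and, as a limiting case, no admitted MF/SS subject is ever scored a responder, power falls from 0.902 to 0.823, 0.697 and 0.519 with 4, 8 and 12 such subjects.

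**5. SAP 3.7.3 against the schedule.** PET/CT can supply nodal and visceral rates for PTCL. Skin and blood rates have no scheduled assessment in PTCL subjects. The sentence also places PTCL in Part 4, whose eligibility section (Protocol 4.1) admits only CTCL.

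**The case against.** The strongest reply is that the mention of CTCL is a drafting slip that the rest of the protocol resolves. The parenthesis points to Appendix A, which keeps MF and SS under CTCL and puts other skin entities, such as "Primary cutaneous gamma delta+ T-cell lymphoma", under PTCL. The words may have been meant for those entities. This is a plausible origin. It does not settle the matter, because Appendix A says its lists are not exhaustive and section 4.1 is the text that governs entry.

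Central pathology is a real safeguard: it would identify an MF/SS subject in the PTCL cohort. It acts after enrollment, and no rule says what to do with the result. The measurable-site requirement narrows the route without closing it. The Simon rule is also not the only input, since the Synopsis lets durability, safety and the competitive landscape influence the move to Stage 2.

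A reader might infer more than the documents support:

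- **That both cohorts are compromised.** The wording adds nobody to the CTCL cohort. At most a subject who fits both bullets is placed elsewhere.
- **That MF/SS subjects in the PTCL cohort would go without skin scoring.** Section 7.14.1 and Appendix D Table 3 are organised by disease, so such a subject could still be assessed as CTCL.
- **That a nodal response could be called in primary cutaneous PTCL while skin disease grows.** That depends on what Lugano requires, which the documents do not reproduce. Skin is part of the physical examination, PET/CT is scheduled, and suspected clinical progression triggers a disease assessment.

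**Conclusion.** The concern holds for the PTCL cohort. Section 4.1 contradicts itself and the protocol's other definitions of PTCL, and no assignment rule resolves the contradiction. Taken literally, it lets MF/SS subjects count in the PTCL Simon decision, where one subject is 5.6 percentage points at Stage 1 and 2.9 at the end.

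The false-positive figures of 0.075 to 0.544 for 4 to 12 MF/SS subjects rest on assumed numbers and response rates. They show sensitivity and do not estimate what happened: nothing in the documents shows an MF/SS subject in the PTCL cohort. The primary safety endpoint and the Simon boundaries are unaffected.

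The SAP 3.7.3 problem is separate and would remain after the eligibility wording is corrected. It is confined to skin and blood rates for PTCL and to the reference to PTCL in Part 4.

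**What to change.** 1. Reconcile the PTCL bullet in Protocol 4.1 with the Synopsis, section 3.3.1 and Appendix A by removing CTCL from it. State that MF and SS subjects are assigned to, and counted in, the CTCL cohort only.
2. Before each stage decision, use the centrally reviewed diagnosis to confirm that the PTCL Simon count contains no MF/SS subjects. Make this check without reference to response, because the trial is open-label and an exclusion made with response known could be driven by outcome. Report any subject removed and fill the place with the next response-evaluable PTCL subject, so that the boundaries still apply to 18 and 35. Removed subjects stay in the Safety Analysis Set.
3. In SAP 3.7.3, limit skin and blood response rates to subjects who have those assessments, and remove PTCL from the reference to Part 4.

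No new response rule and no retrospective skin scoring for primary cutaneous PTCL is needed. The documents do not establish a need for the former, and mSWAT cannot be reconstructed without a baseline score.

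The cost is one wording change and one assignment sentence in the protocol, one check against a review already planned, and one SAP sentence. MF/SS subjects who meet only the PTCL bullet could no longer enter by that route. Sample size and boundaries do not change.
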